As a means of assessing participants' understanding of what the study entails, we will conduct a one-on-one informed consent survey, which asks questions such as, "What illness is being studied in this project?" "Are there any risks to participating in this study?" and "Will you lose any of your benefits if you refuse to participate in this study?" If the participant is unable to answer the questions or demonstrates a lack of understanding, the investigator will review the details of the study again. The survey therefore serves to ensure that participants are actively engaged in the informed consent process. For each participant, we will re-administer the informed consent survey at the beginning of each visit, in order to ensure that the participant is capable of consent throughout the entire study. Participants who are unable to answer all 9 questions on the survey correctly even after additional information is provided will be excluded from the study.

We will acquire written informed consent for all participants using the IRB-approved consent form. All signed forms will be stored in a file cabinet in a locked office.

For individuals who wish to participate in the second protocol (e.g., Protocol B after completing Protocol A), we will take the necessary time to remind participants about the study procedures, risks, and benefits, and answer any questions they may have about the study. We will also re-evaluate whether participants continue to meet the eligibility criteria. However, because Protocols A and B are both part of this same IRB protocol, we will not maintain separate written informed consent forms for the two protocols.

Treatment assignment, and randomization

All subjects, including controls, will receive either cTBS (inhibitory), iTBS (excitatory), or sham TBS in each of the three visits. The order in which they receive a particular type of TMS will be randomized for each subject by the study staff prior to the first TMS administration. The investigators and the research coordinator will not be blinded to the randomized order, since all

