assessments pre- and post-TMS require input solely from the subjects. However, subjects will be blinded as to which mode of TMS they receive at each study visit. Sham TMS will use the exact same procedure with a sham coil, which is designed to induce the same nonspecific sensory effects of TMS (auditory and somatosensory activation) without inducing the neuromodulatory magnetic fields. At the end of each study visit, subjects will be asked to speculate on which mode of TMS (inhibitory, excitatory, or sham) they received as well as the degree of certainty of their judgment so that we can assess the potential contributions of subjects' expectations on their task performance.

V. STUDY PROCEDURES:

All subjects, including healthy controls, will undergo three visits at the MGH Laboratory for Neuropsychiatry and Neuromodulation in the Charlestown Navy Yard Campus, with at least 36 hours separating the visits.

The subject is free to withdraw from the study at any time simply by informing the investigators. Similarly, the investigators may decide to stop the study if the purposes of the study cannot be met (technical difficulties, new information on subject characteristics, etc.).

Summary of Study Procedures

The first visit will include the following procedures (for the second and third visits, the clinical characterization step will be skipped):

Patients:

- Consenting procedures (15-20 minutes)
- Clinical characterization (1-2 hours)
 - Positive and Negative Syndrome Scale (PANSS)
 - Young Mania Rating Scale (YMRS)
 - Montgomery-Asberg Depression Rating Scale (MADRS)
 - North American Adult Reading Test (NAART)
 - Psychotic Symptom Rating Scale: PSYRATS-AH
 - The Behavior Rating Inventory of Executive Function – Adult Form (BRIEF-A)
 - Barratt Impulsiveness Scale (Version 11; BIS-11)
 - Fagerstrom Test for Nicotine Dependence
- Urine toxicology/pregnancy screen (5 minutes)
- Baseline/pre-TMS assessments (15-20 minutes)
 - Interval discrimination task for Protocol A (or repetitive finger-tapping task for Protocol B)
 - N-back working memory task for Protocol A (or multi-source interference task (MSIT) for Protocol B)
 - Flanker task for Protocol A
 - Visual analog scales (VAS) to assess mood and psychotic symptoms
- Transcranial Magnetic Stimulation (TMS) (15 minutes)
 - Excitatory, inhibitory, or sham (order randomized)
- Post-TMS assessments (15-20 minutes)
 - Interval discrimination task for Protocol A (or repetitive finger-tapping task for Protocol B)

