Once the MT is determined, we will apply TBS to our main target: the **cerebellar vermis**. In specific, we will target the posterior vermis (comprised of lobules VI-X), which is believed to subserve cognitive and affective functions (vs. the anterior vermis, comprised of lobules I-V, which is associated with somatomotor functions). From a practical standpoint, the posterior vermis (especially lobules VII-VIII) is also closer to the skull surface and thus will receive more direct TMS modulation (**Figure 4**). Using the Localite TMS neuronavigation system we will co-register the participant's head to his or her MRI, and place the TMS coil over the scalp position that allows direct stimulation of the vermal lobules VII-VIII in the mid-sagittal plane.

[figure not shown]

Figure 4. Mid-sagittal view of the cerebellum. We will apply theta-burst stimulation (TBS) to the posterior cerebellar vermis, directing the coil to lobules VII and VIII, which are closest to the skull surface. Figure from ¹¹³, pp. 241, figure 4.

At this point, the experimental session can begin. In a random order, patients will receive either cTBS (inhibitory), iTBS (excitatory) or sham TBS in each of the 3 sessions. Subjects will be blinded as to which mode of TMS they receive at each study visit. Sham TMS will use the exact same procedure with a sham coil, which is designed to induce the same nonspecific sensory effects of TMS (auditory and somatosensory activation) without inducing the neuromodulatory magnetic fields. At the end of each study visit, subjects will be asked to speculate on which mode of TMS (inhibitory, excitatory, or sham) they received as well as the degree of certainty of their judgment so that we can assess the potential contributions of subjects' expectations on their task performance.

Visual Analogue Scales (VAS)

A visual analogue scale (VAS) is a psychometric response scale, which easily and rapidly allows subjects to self-evaluate the intensity of subjective measures, such as mood and psychotic symptoms. Participants will complete visual analogue scales to indicate their current levels of

depression, anxiety, euphoria, auditory hallucinations, visual hallucinations, paranoia, referential thinking, and delusions of control before and after TMS using RedCap.

Behavioral Tasks

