4. **Multi-Source Interference Task (MSIT)**: the MSIT is a behavioral task that combines multiple dimensions of cognitive interference and decision-making, and other factors such as target detection, novelty detection, error detection, response selection, stimulus/response competition, and task difficulty. For the MSIT, subjects are given a button-press and instructed that the keypad buttons represent one, two, and three from left to right. They are told to use the index, middle, and ring fingers of the right hand to respond. They are instructed that sets of three numbers (1 and/or 2 and/or 3) and/or letters (x) would appear in the center of the screen every 1.75 s, and that one number would always be different from the other two (matching distractor) numbers or letters. Subjects are asked to report, via button-press, the identity of the number that was different from the other two items. Subjects are informed that each session will begin and end with fixation of a white dot for 30s, and that between these times there will be two trial types that would appear in alternating 42 s long blocks. In trials with numbers and letters (control trials), the target number will always match its position on the button-press (e.g. the number "1" will appear in the first [leftmost] position). In contrast, during the trials involving all numbers (interference trials), the target will never match its position. It will be emphasized that they are to "report what the target number is regardless of its position." Further, subjects are informed that in the numbers and letters (control) condition, the target number will always be large, while the numbers only (interference) condition the target number will sometimes be large and sometimes be small (in

actually, unbeknownst to subjects, the number of large target trials and small target interference trials will be equal). For all trials, subjects are instructed to answer as quickly as possible but to make sure that they give the right answer.

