5. **Repetitive finger tapping task (Carroll et al. 2009):** The repetitive finger tapping-task consists of two conditions: (1) tone-paced tapping, and (2) self-paced tapping. In both conditions, a press of the response button is used to calculate the inter-tap interval. Each trial begins with an auditory tone placed at 500 ms inter-tone intervals. In the tone-paced tapping condition, participants are instructed to tap the response button at the same rate as tone. After 12 taps, the tone is discontinued and participants are required to continue tapping at the same rate as the previously presented signal (self-paced tapping). Trials are terminated following 30 self-paced button presses. Error taps are defined as inter-tap intervals 250 ms above or below the 500 ms pacing interval during either the tone or self-paced portion of the trial. A total of 6 error-free trials, or a maximum of 12 trials, signal the completion of the task.

[figure not shown]

Fig 2. Diagram of interval discrimination task. The black bars represent the 50 ms standard tones that establish the intervals of the standard and the comparison time intervals.

Compensation

Subjects will be compensated by check for up to \$200 for completion of a protocol (Protocol A or B). The breakdown of compensation is as follows:

• 1 st Visit (Clinical evaluation, TMS, and pre- and post-TMS assessments)	\$ 75
• 2 nd Visit (TMS and pre- and post-TMS assessments)	\$ 50
• 3 rd Visit (TMS and pre- and post-TMS assessments)	\$ 50
• Protocol completion bonus	\$ 25
	TOTAL \$ 200

Because data from all three visits (sham, excitatory, and inhibitory TMS) are necessary to interpret the results with causal explanatory power, participants will be paid a completion bonus for completing all three visits.

If the subject does not complete the entire study he/she will be compensated for the procedures listed above that were completed. Subjects are informed that it may take up to 4-6 weeks for them to receive their payment.

Should they choose to do so, subjects may participate in both Protocol A and Protocol B. Subjects will be additionally compensated by check for up to \$200 for completion of the second protocol (e.g., Protocol B after completing Protocol A). The breakdown of compensation for Protocol B is as follows:

• 4 th Visit (Clinical evaluation, TMS and pre- and post-TMS assessments)	\$ 75
• 5 th Visit (TMS and pre- and post-TMS assessments)	\$ 50

• 6 th Visit (TMS and pre- and post-TMS assessments)	\$ 50

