Subjects are informed that there is no direct benefit to them from participating in this study. As mentioned in the section on Background and Significance, the potential benefits to society are increased understanding of mood and psychotic disorders, and the role that the cerebellum plays in them, specifically in the abnormalities of time perception, cognition, and mood and psychotic symptoms. The current research, which uses TMS as a tool to investigate with causal explanatory power the role of the cerebellum in psychotic disorders, may provide the basis for the development of TMS as a potential treatment tool in such disorders in the future.

IX. MONITORING AND QUALITY ASSURANCE:

Human Subjects Protections:

See Section VI (Risks and Discomforts) for measures to protect research subjects from the risks associated with the informed consent process, confidentiality, psychiatric evaluations, and TMS procedures.

Independent monitoring of source data

[name], the Principal Investigator (PI), will be responsible for monitoring the validity and integrity of the data, as well as adherence to the protocol. She will be present for the informed consent procedures, assessments, and TMS administration for the first several subjects and closely supervise the training of all study staff involved in carrying out this research. In addition, co-investigator [name], who is a physician, will be on-site at the MGH Laboratory for Neuropsychiatry and Neuromodulation in the Charlestown Navy Yard Campus, to monitor the correct and safe administration of TMS for each subject.

Standard operating procedures (SOP) will be written, routinely followed, and updated as necessary to ensure adherence to the IRB-approved protocol. Any time there is a change in study staff, the PI will again provide direct hands-on training in order to ensure that all procedures are conducted in adherence with the IRB-approved protocol and that the data collected are of high quality, validity, and integrity. Moreover, the PI will meet at least once a week with the study staff to review any issues and data quality. Finally, the PI will be responsible for subsequently signing all consent forms, thereby allowing her to monitor the informed consent process on a consistent basis. The research coordinator and PI will report any minor deviations from the protocol at each yearly continuing review. Major deviations will be reported within 5 working days of the incident's occurrence or detection.

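### Staff are left unblinded to TMS order because only subjects supply the outcome data; this excludes scoring bias but not expectancy cues, which could be reduced cheaply

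*Protocol*

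**What the plan says.** Protocol section IV, under treatment assignment and randomization, sets out a single-blind design. The order is "randomized for each subject by the study staff prior to the first TMS administration". Then: "The investigators and the research coordinator will not be blinded to the randomized order", on the ground that "assessments pre- and post-TMS require input solely from the subjects". On the other side, "subjects will be blinded as to which mode of TMS they receive at each study visit", a sham coil imitates the sound and feel of stimulation, and at the end of each visit subjects guess the mode and rate their certainty.

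Section V describes the outcomes. Participants complete eight mood and psychosis VAS items "before and after TMS using RedCap". The behavioral tasks carry instructions in the passive voice. One MSIT response rule is introduced with "It will be emphasized that they are to", and for finger tapping "participants are instructed to tap the response button at the same rate as tone". Nobody is named as giving these instructions.

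Section IX has the principal investigator attending assessments and stimulation for the first several subjects. It also places a co-investigator on site "to monitor the correct and safe administration of TMS for each subject". Section VII says that study staff assess subjects before, during and after TMS.

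**The concern.** The stated reason answers one question, whether a rater who knows the condition could score it differently, and leaves another open. A subject's effort and self-report can be influenced by the manner, emphasis or encouragement of someone who knows what was just delivered. That remains true when the subject alone presses the buttons or moves the slider.

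Three features make the open question matter:

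- **Direction.** Aim 1 predicts that patients improve after excitatory and worsen after inhibitory TMS, with no significant symptom change after sham. Staff who share that expectation would tend to push results the same way.
- **Type of outcome.** Self-rated mood and psychotic symptoms are the most open to suggestion. Accuracy and reaction time are measured responses and less exposed, but they still depend on effort.
- **Use of the result.** The protocol wants to draw causal conclusions about the cerebellum. That requires the three conditions to differ only in the stimulation.

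**Working it through.** **1. The plan's own figure.** Section VI.D gives 80% power for an effect size of 0.35 in within-patient change with 50 patients. Alpha and sidedness are not stated. With power = Φ(d√n − z) and d√n = 0.35 × √50 = 2.475:

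- one-sided 5%: Φ(2.475 − 1.645) = 79.7% (exact t: 78.7%), which reproduces the figure;
- two-sided 5%: Φ(2.475 − 1.960) = 69.7% (exact t: 67.9%), which does not.

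The blinding point does not depend on this. The 0.35 serves below only as a yardstick.

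**2. Which routes the stated reason closes.**

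| Route for bias | What the documents say | Closed? |
|---|---|---|
| Rater scores differently by condition | Subjects alone supply the data; VAS self-entered in RedCap | Yes |
| Subject recognises the device | Subjects blinded; sham coil imitates sound and feel | Mitigated |
| Cues from staff who instruct or attend outcome sessions | Instructions are given, with emphasis; no one named; investigators and coordinator know the order; principal investigator attends early assessments | No |
| Handling of data by condition | No coded labels described in the protocol or SAP | No |

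**3. What the mode guess does.** It comes after the outcomes, so a change the subject has noticed may shape it. It records belief and prevents nothing. Protocol section VI.C and the SAP list the planned analyses, and neither uses the guess or the certainty rating.

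**4. Illustration of size.** The inputs are:

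- n = 50 complete patients. Section III expects fewer usable data sets than are enrolled, but gives no rate.
- No true effect.
- A cue-induced shift of b SD in the within-patient contrast of pre-to-post change, active against sham. The documents give no value, so b is assumed over a range. A cue that acts equally before and after TMS cancels in the change and is not counted.
- A two-sided 5% paired t-test, as a proxy for the planned Friedman's test (VAS) and mixed models (other outcomes).

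The rejection probability comes from the non-central t distribution with n − 1 degrees of freedom and non-centrality b√n. For n = 50 the non-centrality is 0.10 × 7.071 = 0.71, 0.15 × 7.071 = 1.06 and 0.20 × 7.071 = 1.41.

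| Assumed shift b (SD) | n = 50, two-sided | n = 50, one-sided 5% | n = 30 (assumed), two-sided |
|---|---|---|---|
| 0 | 5.0% | 5.0% | 5.0% |
| 0.05 | 6.4% | 9.7% | 5.8% |
| 0.10 | 10.7% | 17.2% | 8.3% |
| 0.15 | 18.0% | 27.5% | 12.5% |
| 0.20 | 28.4% | 40.1% | 18.5% |

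A shift of 0.20 is 0.20 / 0.35 = 57% of the protocol's stated detectable effect.

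**The case against.** The design is openly single-blind, gives its reason, and belongs to a pilot. The VAS is typed in by the participant, the tasks record button presses, subjects are blinded, the sham coil is realistic, and belief about the mode is collected at every visit. The rates above are also no evidence of bias: the shifts are assumed, and the table only restates the power curve of a test that is not the planned one. All of this stands, and it limits the point to a route left open.

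Three stronger readings are tempting but go beyond the documents:

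- **A reader might infer that unblinded staff give the VAS and the task instructions.** The VAS is self-completed, and no one is named as giving instructions. The coordinator's described work is recruitment, screening and deviation reporting. Delivery by unblinded staff is plausible, not stated.
- **A reader might infer that existing roles would let cues be removed altogether.** A research assistant is mentioned in section IV and an on-site co-investigator in section IX, but their roles in the outcome sessions are not described and the TMS operator is not named. Whoever sets the coil and pulse pattern must know the mode. Section VII gives TBS durations of 40 to 190 seconds, so session length may itself be a cue that staff blinding does not touch.
- **A reader might infer that any such bias would be wholly inseparable from a TMS effect.** The guess data allow a partial check. They do not settle the matter, and no such check is planned.

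What the objection does not answer is the reasoning itself: subject-only input is a sound argument against scoring bias and no argument against cues.

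**Conclusion.** The stated justification for leaving staff unblinded is insufficient. It leaves a route by which expectancy could move the self-rated symptom scales, and to a lesser degree the effort-dependent tasks, in the hypothesised direction. The existing safeguards mitigate or measure this without preventing it, and the one that measures it has no planned analysis.

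The size is unknown. Under the assumptions in the working (50 complete patients, no true effect, two-sided paired t-test as proxy), shifts of 0.10 to 0.20 SD would give a false-positive rate of about 11% to 28% in place of 5%. The same SD shift should not be presumed for reaction times and for self-rated mood.

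The documents do not show that bias will occur, or that unblinded staff run the outcome sessions. They show that nothing in the plan rules this out. A change is worthwhile because it is cheap, not because a defect in the data has been demonstrated.

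**What to change.** Replace the blinding rule in protocol section IV, and add to the analysis plan, as follows:

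1. **Order list.** Name who draws and holds the order, and restrict it to whoever sets the coil and pulse pattern.
2. **Outcome sessions.** State who attends the pre- and post-TMS tasks and VAS, and keep that person unaware of the mode where existing staffing allows.
3. **Instructions.** Use fixed on-screen text for every task, identical at every visit.
4. **Data handling.** Clean and score the data under coded condition labels, and reveal them only after scoring is locked.
5. **Guess data.** Prespecify a sensitivity analysis using guessed mode and certainty. Present it as a sensitivity analysis and not a correction, because the guess follows the outcomes.

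The cost is protocol and SAP wording and a sealed or electronic order list. The one practical downside is that the person attending outcomes at a visit should not be the TMS operator. Where that cannot be arranged, items 3 to 5 still apply and need no extra staff. Items 4 and 5 can be adopted even after data collection, provided the condition labels have not yet been used in analysis.

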The cerebellum plays a major role in information processing but it has not been considered a treatment target for studies of major mental illness. The goal of this study is to investigate the impact of modulating cerebellar activity on mood and psychotic symptoms in patients as well as the closely related domains of executive function and time perception. We will study up to 100 healthy subjects and up to 100 psychosis patients (i.e., schizophrenia, schizoaffective disorder, and psychotic bipolar disorder). In sham-controlled crossover design, we will present validated cognitive paradigms and clinical measures to subjects before and after TMS. We hypothesize that abnormally reduced activity in the cerebellum contributes to the abnormalities in patients and therefore cerebellar stimulation will normalize outcome measures. The circuitry of the cerebellum is complex and the main projection neurons in this brain region (Purkinje cells) are inhibitory. Therefore, we will test the specificity of our hypothesis by including an "inhibition" TMS condition which we hypothesize will worsen the outcome measures. The specific aims are to:

Aim 1: Investigate the role of the cerebellum in abnormalities of time perception, cognition, and mood and psychotic symptoms by evaluating these functions before and immediately after excitatory, inhibitory, or sham TMS applied to the cerebellum in patients with psychosis and in healthy control participants. Participants will undergo three study visits, one for each of the three TMS conditions. At each study visit, we will measure the following before and after TMS:

- a) **Time perception:** We will measure time perception using a time perception task. *Hypothesis:* Compared with healthy control participants, patients with psychotic disorders will have impaired timing perception (i.e., higher number of errors and/or greater inter-trial variability in the task) both at baseline and after sham TMS. We predict that the abnormalities in patients will further worsen after inhibitory TMS, and improve after excitatory TMS.

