As part of the clinical evaluation, we will also ask female participants about and record the first date of their last menstrual period (LMP). Clinical symptoms and cognitive functioning can vary according to the phase of the menstrual period. We will evaluate what phase of the menstrual cycle a female participant is in at the time of each study visit so that we can potentially control for any associated confounding effects.

Similarly, nicotine is well-documented to affect cognitive functioning, and is an important variable to control for. Therefore, we will administer a Fagerstrom Test for Nicotine Dependence in all research participants. For individuals who are smokers, we will record the time of the participant's last cigarette prior to each study visit.

For all subjects, during each and every visit, urine toxicology screens will be used to assess for current substance use, and urine pregnancy tests in women of child-bearing age to determine if she is

pregnant (and thus is ineligible to participate in the study).

Scheduling of study visits

As mentioned before, this will be a cross-over design, in which participants will undergo excitatory, inhibitory, and sham TBS over three study visits, separated by at least 36 hours. The order in which participants receive excitatory vs. inhibitory vs. sham TMS will be randomized.

The effects of a single session of rTMS are acute and reversible, and usually recede in less than an hour. Nonetheless, the study visits will be separated by at least 36 hours in order to provide more than ample time for the brain to return to homeostatic balance and ensure that there are no potential residual TMS effects from the previous study visit.

If scheduling permits, participants may be able to complete all three study visits in as short as one week. However, to accommodate scheduling flexibility for research participants, we will allow up to two months for participants to complete all three study visits within a single protocol.

Participants will participate in one of two protocols, Protocol A (**Figure 2**) or Protocol B (**Figure 3**). The two protocols are identical except that they involve different time perception and executive function tasks. Specifically, the tasks in Protocol A are the interval discrimination task, flanker task and the N-back working memory task, while those in Protocol B are the repetitive finger tapping task and the multi-source interference task (MSIT).

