1. **N-back task**: The n-back task engages working memory, a cognitive construct that falls under executive function. Deficits in working memory are observed across psychiatric diagnoses. In the n-back task, subjects are presented with a series of stimuli, such as words or numbers. The subjects are prompted to indicate whether the currently presented stimuli are the same as the stimuli presented n-stimuli previously. For instance, a 2-back task would ask the subjects to indicate whether the current stimuli was identical to that presented two previously. Outcome measures of interest include reaction time and accuracy.
2. **Interval discrimination task (Papageorgiou et al., 2013)**: This experimental procedure requires subjects to perform time interval comparisons. In each trial, two tones separated by 1200 ms (the standard interval) are first presented, followed by a 1 s delay, and then a comparison pair of tones. For some trials, the time interval of the second pair is equal to the time interval of the first pair (E-condition). In another set of trials, the time interval of the second pair is longer than the standard interval (L-condition), while in the remaining trials, the time interval of the second pair is shorter than that of the first pair (S-condition). The order of the conditions in the trials will be ad hoc randomized and afterwards kept constant for all subjects. After each trial, subjects will be asked to identify whether the time interval of the subject was equal, longer, or shorter than that of the first pair of sounds. Each subject's performance will be evaluated through the overall percentage of correct responses (O), as well as the percentage of correct responses in the L, S, and E conditions.
3. **Flanker task (Holmes et al., 2008)**: The flanker task is a measure of attention and inhibitory control. In the task, subjects must attend and respond to a certain stimulus that is surrounded ("flanked") by distracting stimuli. The stimuli are most commonly arrows. The flanking arrows can either have the same or opposing orientation as the central stimulus. Outcome measures of interest include accuracy and reaction time.

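### The interval discrimination task appears to reuse one fixed trial order at all six runs per participant; any learning of it would enter raw pre-to-post changes and, if groups learn at different rates, the patient-control comparisons after sham and in change

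*Protocol*

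**What the plan says.** Protocol section V, Behavioral Tasks, item 2 describes trials in which the comparison interval is equal to, longer than or shorter than the standard. It then says: "The order of the conditions in the trials will be ad hoc randomized and afterwards kept constant for all subjects". The score is percent correct, overall and for each of the three trial types.

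Section II, Aim 1 sets the repetition: "Participants will undergo three study visits, one for each of the three TMS conditions", and "At each study visit, we will measure the following before and after TMS". Figure 2 shows the task in both positions at every Protocol A visit.

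Section V, Scheduling of study visits, requires at least 36 hours between visits. The purpose given is to "ensure that there are no potential residual TMS effects from the previous study visit"; practice is not mentioned. If scheduling permits, "participants may be able to complete all three study visits in as short as one week"; the limit is two months. "The order in which participants receive excitatory vs. inhibitory vs. sham TMS will be randomized"

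Aim 1a predicts impaired timing in patients relative to controls "both at baseline and after sham TMS. We predict that the abnormalities in patients will further worsen after inhibitory TMS, and improve after excitatory TMS".

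Protocol section VI.C analyses the pre-to-post change by diagnosis and TMS type. The SAP uses a mixed model with condition, time and their interaction. Neither names a visit, period or exposure term. No alternate trial list or practice run is described in either document.

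**The concern.** Giving every subject the same order is sensible in itself: both groups then face identical material. The difficulty is reuse within a subject. A remembered answer and a correct interval judgement score the same, so percent correct cannot separate memory for the list from timing.

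Two kinds of result are exposed.

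- **Raw change within one condition.** Aim 1a words its predictions as worsening after inhibitory and improvement after excitatory stimulation, and section VI.D puts the main interest in change within the psychosis group. A practice gain would flatter the excitatory visit, mask worsening at the inhibitory visit and make sham look active. In the SAP model it would sit in the time effect.
- **Patients against controls once the task has been repeated.** Diagnosis is not randomised, so randomising TMS order gives no protection here. The protocol expects poorer executive function in patients and notes working-memory deficits across diagnoses, so unequal learning is plausible on its own premises. A difference in learning could then be read as a difference in timing.

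**Working it through.** **The plan's own figures.** Neither document gives a figure for practice. The nearest number is in section VI.D: 80% power with 50 patients and an effect size of 0.35. A paired t calculation gives 78.7% one-sided and 67.9% two-sided at 5% (the plan states neither alpha nor sidedness). It makes no allowance for practice, and nothing below depends on it.

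**Exposures.** 3 visits x 2 runs = 6. The post-sham run is exposure 2, 4 or 6. With each visit equally likely to be sham, the mean is (2 + 4 + 6)/3 = 4, so three earlier runs on average.

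**Spacing.** Between the pre and post runs of a visit come the rest of the battery (15 to 20 minutes in all, including the task itself) and 15 minutes of TMS. By the stated timings that is more than 15 and less than 35 minutes.

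**Illustration (all values assumed; none is in the documents).** Gain from run 1 to run 2: 4 percentage points. Each later gain is 0.6 of the one before: 2.4, 1.44, 0.864, 0.52. The SD of a visit's change is 8 points. There is no TMS effect. Cumulative gain in points:

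| Visit | Pre | Post | Gain within visit |
|---|---|---|---|
| 1 | 0 | 4.00 | 4.00 |
| 2 | 6.40 | 7.84 | 1.44 |
| 3 | 8.70 | 9.22 | 0.52 |
| Mean | 5.03 | 7.02 | 1.99 |

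**Condition contrasts.** Under randomised order each condition has the same expected gain, 1.99 points. The expected learning bias in active minus sham is 1.99 − 1.99 = 0. Simple randomisation leaves chance imbalance. The variance of the three gains is 2.17, so the SD of the imbalance at n = 50 is √(3 x 2.17/50) = 0.36 points.

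**Rejection rates with no TMS effect** (4,000 simulated trials, two-sided 5%):

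| n | Learning | Single-condition pre-post test | Active vs sham change |
|---|---|---|---|
| 50 | none | 5.4% | 4.8% |
| 50 | as above | 41% | 5.5% |
| 50 | doubled | 90% | 5.3% |
| 30 | as above | 25% | 5.1% |
| 30 | doubled | 70% | 5.0% |

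**Group comparisons.** Suppose patients learn half as much as controls. The patient-control gap created by learning alone is then:

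- first pre-TMS run: 0.5 x 0 = 0
- pre-TMS runs averaged over visits: 0.5 x 5.03 = 2.5 points
- after sham: 0.5 x 7.02 = 3.5 points
- change score: 3.5 − 2.5 = 1.0 point

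With equal learning every gap is 0. With gains doubled, the post-sham gap is 7.0 points and the change gap 2.0. If patients learned more than controls, the sign would reverse.

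This illustration does not divide learning into list-specific and general practice. New lists would remove only the first.

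**The case against.** Much of the opposing case stands.

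- **Reuse is not express.** The sentence speaks of constancy across subjects. It does not say that one subject's six runs share the order. That is the natural reading, since no other order is described, but it needs confirming.
- **Learning is not shown.** The number of trials is not given, the order is random and no feedback is described. Someone who recalls the list may recall their own earlier errors, which need not raise accuracy. One week is the fastest schedule, not the usual one.
- **The post-sham level comparison is a stated hypothesis without a stated test.** Section VI.C compares changes, and the SAP model names no diagnosis term. In the change score the illustrative bias is 1.0 point, not 3.5.
- **Ordinary practice over six runs would act in the same way,** and new lists would not remove it.

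A reader might go further and infer that sequence learning confounds the TMS effect itself. The documents do not support that. The planned comparison of changes across conditions and the condition-by-time term are protected in expectation by the randomised order, and their null rejection rate stays near 5% even with substantial assumed learning. Nor do the documents show that scores would reach a ceiling (no baseline accuracy is given), or that the association between timing and symptoms in Aim 2 is biased. That would need memory for the list to be related to symptoms; otherwise it adds noise.

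**Conclusion.** The point holds in a limited form. On the natural reading, one trial order is met six times by each Protocol A completer, with no alternate list and no model term for repetition. If the order is partly learnable, raw single-condition changes contain the gain. If learning rates differ by diagnosis, so do the post-sham comparison of patients with controls and the group difference in change. The active-versus-sham change contrast and the condition-by-time term are safe in expectation, and the first pre-TMS group comparison precedes any exposure.

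The size cannot be derived from the documents. Over the assumed range, from equal learning to a first gain of 8 points with patients learning half as much, the added gap runs from 0 to 7.0 points after sham and from 0 to 2.0 points in change. These figures show how the bias would arise; they do not estimate it. The case for acting is that the remedy costs almost nothing, not that bias has been demonstrated.

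**What to change.** First, state whether a subject's six runs share one order. If they do, replace the sentence in item 2 with wording such as: six trial orders, each with the same numbers of equal, longer and shorter trials and the same comparison intervals, will be generated in advance; each participant will receive a different order at each of the six administrations, rotated by Latin square, with the same set used in both groups. Assign the rotation independently of the TMS sequence, so that list and condition are not linked.

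Second, because general practice remains, add visit to the models in Protocol section VI.C and the SAP, with its interaction with time and, where groups are compared, with diagnosis. Visit by time identifies all six runs.

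The cost is five more lists in the task script, one protocol sentence and a few model terms, with no extra visits or participants. The downside is slight variation between lists, which the rotation balances.

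If data have already been collected with one order, use the visit terms and report that the order was repeated. That adjusts for practice as a whole but cannot separate memory for the list from timing.
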